Hemostatic effect is determined by dose of oxymetazoline instilled by the surgeon.

Methods:

Thirty patients of [name] who will undergo functional endoscopic sinus surgery, turbinate surgery or adenoidectomy and are anticipated to receive oxymetazoline-soaked pledgets for hemostasis will be enrolled.

Patients ages 2 through 18 yrs. will be enrolled if they are scheduled for

- 1) Functional endoscopic sinus surgery (ten patients)
- 2) Turbinate reduction (with or without tonsillectomy and/or adenoidectomy) (ten patients)
- 3) Adenoidectomy (ten patients)

Patients will be excluded if they have been treated with oral decongestants or antihistamines within 24 hours of surgery, are taking anticoagulants, have a history of nasal trauma within past 3 months, have a history of epistaxis within past 3 months, have a history of hypertension or cardiac disease, or are allergic to oxymetazoline.

There will be no change in the conduct of the general anesthetic care related to the study protocol. Our usual practice will be followed. For premedication, midazolam (0.5 mg/kg to a maximum of 15 mg) will be administered 15-45 minutes prior to the procedure at the discretion of the attending anesthesiologist. An inhalation induction with sevoflurane or an intravenous induction with propofol will be performed by the attending anesthesiologist and titrated to attempt to maintain the bispectral index (BIS) between 40 and 60 to ensure adequate and similar depth of anesthesia. It will not be considered a protocol violation if the BIS is not maintained at this level. Fluid will be administered to

attempt a total of 15 ml/kg for procedures less than 1 hr or maintenance plus replacement for procedures greater than 1 hr. It will not be considered a protocol violation if this amount of fluid is not infused.

Blood pressure and heart rate and will be recorded at 5 min intervals until discharge from PACU or final blood draw, whichever comes first.

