The surgeon will place oxymetazoline-soaked pledgets according to usual practice. [name] will make two different observations to assess the amount of bleeding and ease of hemostasis (10)

- 1) A four point scale to record subjective bleeding following removal of pledgets

- 0= none, 1= minimal/restricted, 2=moderate/diffuse ooze, 3=severe/brisk
- 2) A six point scale to assess ease of hemostasis
1=very easy, 2=easy, 3=usual, 4=some effort required, 5=difficult, 6=extremely difficult

Blood pressure and heart rate and will be retrieved from EPIC for analysis

Prior to the study Drs. [name] & [name] determined that 10 pledgets in 15 ml of oxymetazoline (1.5 ml per pledget) provided the necessary amount of oxymetazoline for clinical use. The number of pledgets placed will be recorded at the time of insertion. If placement is separated by greater than five minutes, then this will be recorded as a separate event. The volume at each time point and the total dose will be recorded. Age-matched, procedure matched control patients not receiving oxymetazoline will be used for comparison. We will do a retrospective chart review of the control patients for hemodynamic parameters.

Statistical Analysis:

Compare the incidence of hypertension using systolic blood pressure and mean arterial pressure criteria using age adjusted normative tables

Compare the incidence of bradycardia defined as HR < 60 bpm, or tachycardia defined as HR>100

Compare the use of vasodilators for the treatment of hypertension

Compare the use of atropine/glycopyrrolate for the treatment of bradycardia

Compare the volume of oxymetazoline instillation and hemodynamic changes

Measure the serum level of oxymetazoline at approximately 5 (3-6 min), 10(8-12 min), 20(18-22 min), 45 (30-60 min), 90 (75-120 min) and 150 (135-240 min) minutes using the protocol specified above.

Compare the degree of bleeding and the ease of hemostasis using the subjective rating scale by the single surgeon observer.

All demographic and parametric data will be presented as mean (\pm SD). Normally distributed interval data will be analyzed using unpaired t-test. Nominal or ordinal data will be analyzed using Chi-squared contingency table or a Fisher's exact test with Yates correction factor. A $P < 0.05$ will be used to express statistical significance.

REFERENCES:

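### The plan does not secure equal reading frequency or equal observation time in treated children and chart-review controls, so the compared incidences of hypertension, bradycardia and tachycardia can differ without any drug effect.

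*Combined protocol and SAP*

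**What the plan says.** All references are to the combined protocol and SAP.

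- **Enrolled children, schedule (Methods).** "Blood pressure and heart rate and will be recorded at 5 min intervals until discharge from PACU". The same sentence adds a second limit, the last blood sample, and the earlier of the two ends the recording.
- **Enrolled children, source (Methods, after the bleeding scales).** "Blood pressure and heart rate and will be retrieved from EPIC for analysis".
- **Controls (end of Methods).** "Age-matched, procedure matched control patients not receiving oxymetazoline will be used for comparison". Their values are to come from existing charts: "We will do a retrospective chart review of the control patients for hemodynamic parameters". No interval, start, end, minimum number of readings or number of controls is given.
- **Comparison (Statistical Analysis).** "Compare the incidence of hypertension using systolic blood pressure and mean arterial pressure criteria using age adjusted normative tables" and "Compare the incidence of bradycardia defined as HR < 60 bpm, or tachycardia defined as HR>100". Nominal data go to a chi-squared or Fisher's exact test. Nothing says how many abnormal readings, or for how long, make a case.
- **Period of interest (Specific Aims/Objectives).** The primary objective covers the OR and the PACU up to phase 1 discharge. It does not mention the final blood draw as an end point.

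**The concern.** An incidence built on threshold crossings depends on how often and how long a child is observed. If a child counts as hypertensive once any reading passes the limit, each further reading is another chance to become a case. One group has a prospective schedule and its own stopping rule. The other was charted before the study, under no study rule. Nothing brings the two series to the same spacing or the same end point, and the planned tests take no account of the number of readings.

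These incidence comparisons serve the primary objective. With 30 treated children and unadjusted tests, a reader of the results could not separate an effect of oxymetazoline from a difference in how the two groups were recorded.

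**Working it through.** **The plan's own figures.** There is no power calculation, event rate or SD to reproduce. The only design figure is 30 treated patients (10 + 10 + 10 by procedure), which adds up.

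**Inputs from the document.** 5-minute spacing for enrolled children; recording ends at PACU discharge or the final draw (nominally 150 min, range 135–240); no schedule for controls; no case rule.

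**Assumed, not in the document.** Any single reading over the limit makes a case; 15-minute control charting; 90 min of PACU; 60 min of OR; 30 controls; no drug effect. Readings are in z-units with total SD 1 and between-child SD 0.7, so within-child variance is 1 − 0.49 = 0.51. Within-child error is first-order autoregressive. The limit is the 95th percentile (z = 1.645), so each reading has a 5% chance of exceeding it.

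**Step 1: direction of the mechanism.** For k independent readings, P(at least one over) = 1 − (1 − p)^k. Ninety minutes holds 90/5 = 18 readings or 90/15 = 6. With p = 0.05, 1 − 0.95^18 = 60% and 1 − 0.95^6 = 26%. Real readings cluster within a child, so these gaps are too wide; step 2 allows for that.

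**Step 2: correlated readings.** Simulation of 200,000 children; share with any reading over the limit, treated v control:

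| Correlation over 5 min | PACU only, 5-min v 15-min | OR at 5 min in both, then PACU 5-min v 15-min |
|---|---|---|
| 0 | 33% v 19% | 40% v 33% |
| 0.5 | 29% v 18% | 37% v 31% |
| 0.9 | 17% v 13% | 22% v 19–20% |

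At 30 v 30, two-sided Fisher's exact test at 0.05 then rejects falsely in about 16–17%, 11% and 3% of trials (PACU only) and about 5%, 5% and 3% (OR plus PACU). With identical grids it rejects in about 2–3%.

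**Step 3: a different parameter set.** Taking 150 min, 15-minute control charting throughout, per-reading exceedance of 2% or 5%, between-child variance share of 0.3 or 0.5, and correlation of 0.5 or 0.8, incidence is 14.7–48.2% at 5-minute and 10.2–30.1% at 15-minute spacing. Fisher's test rejects falsely in 2.7–21.5%.

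**Step 4: the opposite direction.** Return to the step 2 model at correlation 0.5 and read both groups every 5 minutes, but stop treated recording at 90 of 150 min (18 v 30 readings). Incidence is 29% treated v 37% control.

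**Step 5: the null case.** With the same 5-minute grid and window in both groups, expected incidences are equal and the bias is nil.

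**Step 6: a summary that does not depend on spacing.** In the step 2 model, the mean per-child proportion of readings over the limit is 5% v 5% at every correlation tried.

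**The case against.** A reader might infer that treated children have more readings than controls, and hence that the comparison is tilted toward finding an oxymetazoline effect. The documents do not support that. They never say how often controls were charted. Treated values are also retrieved from EPIC, and anesthetic care follows usual practice, so the 5-minute interval may simply describe routine charting, particularly in the OR. The final-draw clause can shorten the treated window, which works the other way. That clause bites only if a child is still in the PACU after the last draw, which is also unknown.

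A reader might also infer that closer recording leads to more use of vasodilators or atropine/glycopyrrolate. Nothing in the documents shows that recording frequency changes how closely clinicians watch or treat, so the point does not extend to those comparisons.

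Two further limits stand. The any-reading case rule is an inference, because the plan says only incidence. And the plan also allows t-tests on interval data; regular thinning does not shift an average as it shifts an any-crossing count, so not every hemodynamic comparison is exposed. The PACU-only figures are the less favorable illustration, and the gap narrows once equally charted OR time is included.

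What this leaves untouched is the gap itself. A shared database does not imply equal charting frequency. Two possible biases of unknown size and opposite direction cannot be relied on to cancel.

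**Conclusion.** The point holds as a gap in the plan, not as a demonstrated bias in a known direction. Nothing requires equal reading frequency or an equal window in the two groups, and the case definition and tests do not protect against inequality in either.

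Under the stated assumptions at correlation 0.5, the spurious difference is 11 percentage points in PACU-only incidence (29% − 18%), 6 points over OR plus PACU (37% − 31%), and 8 points in the other direction if only the treated window is cut short (29% − 37%). It is nil if both groups were charted every 5 minutes over one window. All of these rest on an assumed control interval, period lengths, correlation and single-crossing rule, none of which the documents give. The plan should settle the matter before control charts are compared.

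**What to change.** 1. State the case rule: how many readings, or what duration, over the limit make a case of hypertension, bradycardia or tachycardia.
2. For OR and PACU separately, set one start and one end point for all members of each matched set, anchored on events that both charts contain (for example, PACU arrival), with the end at the shortest member's window. Reconcile the end of recording in Methods with the phase 1 discharge named in the primary objective.
3. Within that window, take the reading nearest each point of a common grid at the coarser spacing found in the set, and compute incidence from those readings. Alternatively, compare the per-child proportion of readings over the limit. If charting becomes denser when values are abnormal, proportion of time is the safer version.
4. Report readings per hour and observation time by group, so that a reader can see whether the groups were recorded alike.
5. Keep the full 5-minute series for the treated-only analyses of dose and plasma concentration.

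The cost is SAP wording and a little programming, with no new data. The downside is that some treated readings leave the between-group comparison, so brief peaks may be missed, equally in both groups. If charting proves equal, little is lost.

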Giannakopoulos studied the cardiovascular effects and pharmacokinetics of an intranasal 3 percent tetracaine/0.05 percent oxymetazoline spray at two different dose levels in adult dental patients. (8) A small decrease in heart rate and a small increase in diastolic blood pressure was noted. Serum levels of oxymetazoline were measured and a half-life of 1.72 to 2.32 hours was noted. No similar pharmacokinetic studies have been reported in children. Latham and Jardine reported oxymetazoline-induced hypertension in a 4-year-old child. (9) They also sought to investigate alterations in the amount of medication delivered based on the delivery method. There was up to a 75-fold increase in the volume of medication administered when the bottle was held inverted. Squeezing the bottle in the upright position resulted in a mist with the delivery of $28.9 \pm 6.8 \mu\text{l}$ of fluid. The amount delivered was effort independent. When the bottle was inverted and squeezed, the volume administered was effort dependent.

Current practice at NCH is to soak nasal pledgets with full strength oxymetazoline and insert a varying number of pledgets on the nasal turbinates or into the sinuses for hemostasis, or on the adenoid bed.

This proposed study will assess the hemodynamic effects and measure the systemic absorption of topically applied oxymetazoline in patients undergoing functional endoscopic sinus surgery, turbinate surgery, or adenoidectomy.

Specific Aims/Objectives:

The primary objective is to determine the perioperative hemodynamic effect of oxymetazoline applied topically for vasoconstriction in patients undergoing functional endoscopic sinus surgery, turbinate surgery or adenoidectomy using blood pressure and heart rate intraoperatively (OR) and postoperatively (PACU) until discharge from phase 1 of the PACU.

A secondary objective is to measure the plasma concentrations of oxymetazoline at discrete time periods from instillation and correlate with hemodynamic effects, as well as determine the rate of decline in levels as a function of time.

A secondary objective is to assess the degree of bleeding and ease hemostasis rated by a single observer to minimize variability.

Hypotheses:

Instilled oxymetazoline causes an increase in blood pressure in the intraoperative and postoperative period and, though absorption is rapid and variable, effects are related to serum level of oxymetazoline.

The decline in hemodynamic effect and serum levels is a function of time.

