Blood samples will be drawn at approximately 5 (3-6 min), 10 (8-12 min), 20 (18-22 min), 45 (30-60 min), 90 (75-120 min) and 150 (135-240 min) minutes via a second IV, placed after the induction of anesthesia. Each sample will be collected in a 3 ml heparin green-top tube. The maximum volume per patient is 18 ml, which is 1.2 tablespoons of blood or approximately 1.5% of the total blood volume in a 2 yr old. This a fraction of the usual blood loss associated with sinus, turbinate, and adenoid surgery. If patient is ready to be discharged from PACU prior to the completion of blood sampling, the sampling will be discontinued and the second IV will be removed.

Plasma Samples

Collection

1. Collect blood sample to analyze oxymetazoline plasma concentrations using a 3 mL - draw green-top Vacutainer® Hemogard collection tube containing heparin.
2. Immediately following collection, gently invert blood sample 8-10 times to mix the anticoagulant in the tube with the blood and place on ice. Separate plasma using standard centrifugation procedures (centrifuge tube approximately 10-15 minutes at 2000g). If plasma has not completely separated, re-centrifuge the specimen for an additional 3-4 minutes. Transfer duplicate plasma aliquots of approximately equal volume. Samples will be stored immediately after plasma separation and may be kept in a dedicated refrigerator at $+5 \pm 2^{\circ}$ C.
3. A minimum of 250 μ L plasma will be required.

Processing

1. Transfer duplicate plasma aliquots of approximately equal volume, using standard laboratory technique, into two appropriately-labeled polypropylene tubes (A and B) with screw caps.
2. Labels should be secured to each storage tube using a strip of tape wrapped completely around the tube. Labels should contain the following information: Protocol and study numbers; subject number; study day and time of sample collection; aliquot (Aliquot A or Aliquot B); sample ID (as provided by Sponsor) and biological matrix to be analyzed (whole blood).

Storage

1. Store plasma aliquot A and plasma aliquot B samples in a GLP-compliant freezer at -70° C. Plasma should not be stored at room temperature at all and at $+5 \pm 2^{\circ}$ C for no longer than 24 hours.

Plasma aliquot B samples will remain stored at the Clinical Study Unit as a backup in a GLP-compliant freezer at -70° C, until shipment is requested.

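### Sampling stops at PACU discharge readiness with no final draw as the line is removed, so short-stay children lose late levels needed for the rate-of-decline objective

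*Combined protocol and SAP*

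**What the plan says.** The blood-sampling paragraph of the Methods schedules six draws. The first three are at about 5, 10 and 20 min, and the rest are at "45 (30-60 min), 90 (75-120 min) and 150 (135-240 min) minutes via a second IV, placed after the induction of anesthesia". On volume it says: "Each sample will be collected in a 3 ml heparin green-top tube", with a stated maximum of 18 ml per patient.

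The stopping rule follows: "If patient is ready to be discharged from PACU prior to the completion of blood sampling", then "the sampling will be discontinued and the second IV will be removed". Nothing elsewhere in the document provides for a sample at that moment.

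Under Specific Aims/Objectives, a secondary objective is to "determine the rate of decline in levels as a function of time". The Hypotheses add: "The decline in hemodynamic effect and serum levels is a function of time". The Background reports, from a study of an intranasal spray in adult dental patients, that "a half-life of 1.72 to 2.32 hours was noted", and says that no similar pediatric study has been reported.

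The Statistical Analysis section says only that levels will be measured at the six times. It gives no model for the decline and no handling of profiles cut short.

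**The concern.** A decline rate is estimated mainly from the late samples. The schedule is already short relative to the cited half-life, so there is little late information to spare. The rule gives it up at the moment when a last sample is easiest to obtain: the second IV is still in place and the blood is within the volume already allowed.

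The loss is also not random, because it depends on the time from instillation to discharge readiness. Late levels therefore come only from children with longer stays. At stake is the precision of the decline rate, and in the shortest stays whether a child contributes usable information on decline at all. The primary hemodynamic objective does not rest on these draws.

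**Working it through.** **The plan's own figure.** 6 draws × 3 ml = 18 ml, which matches the stated maximum.

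**Coverage in half-lives.** The cited half-life is 1.72 × 60 = 103.2 min to 2.32 × 60 = 139.2 min.
- To 150 min: 150/139.2 = 1.08 and 150/103.2 = 1.45.
- To 240 min, the end of the last window: 240/139.2 = 1.72 and 240/103.2 = 2.33.
- From 45 to 150 min: 105/139.2 = 0.75 and 105/103.2 = 1.02.

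**What the windows leave open.** The late windows are 30–60, 75–120 and 135–240 min. Readiness is taken on the same clock as the draws.
- Ready before 75 min: the 90- and 150-min draws are lost.
- Ready before 135 min: the 150-min draw is lost.
- Ready at 60–75 or 120–135 min: no window is open, so no scheduled draw can be taken on leaving.
- Ready at 75–120 min or from 135 min: a due draw can be taken in window, but the text does not call for it.

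**Precision of one child's slope.** For log concentration declining linearly in time, SE = s/√Sxx, where Sxx = Σ(t − mean t)² and s is the residual SD on the log scale. Ratios of SEs do not depend on s. The plan does not say which sample starts the decline phase, so starts at 20 and 45 min are both shown for readiness at 130 min.

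| Case | Without exit draw (Sxx) | With exit draw (Sxx) | SE ratio | Cut |
|---|---|---|---|---|
| Ready at 130, decline from 45 | 45, 90 (1012.5) | 45, 90, 130 (3616.7) | 0.53 | 47% |
| Ready at 130, decline from 20 | 20, 45, 90 (2516.7) | 20, 45, 90, 130 (7118.75) | 0.59 | 41% |
| Ready at 130, previous draw at 120 | 45, 120 (2812.5) | 45, 120, 130 (4316.7) | 0.81 | 19% |
| Ready at 70, decline from 20 | 20, 45 (312.5) | 20, 45, 70 (1250) | 0.50 | 50% |

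If decline is counted only from 45 min, a child ready at 70 min has one point and no slope. The exit draw gives two points: a slope with no residual degrees of freedom.

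**Against a complete profile.** The set 20, 45, 90, 150 has Sxx = 9768.75.
- Stopping after 90 min: √(9768.75/2516.7) = 1.97 times the full-profile SE. With an exit draw at 130 min: √(9768.75/7118.75) = 1.17 times.
- Stopping after 45 min: √(9768.75/312.5) = 5.59 times. With an exit draw at 70 min: √(9768.75/1250) = 2.80 times.

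**Absolute size, on an assumed residual CV.** The documents give no CV. With s = √ln(1 + CV²) and k = ln 2/half-life, the relative SE of one child's k over the cited half-lives is:

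| Samples | CV 10% | CV 20% | CV 30% |
|---|---|---|---|
| 20, 45, 90, 150 | 15–20% | 30–40% | 44–60% |
| 20, 45, 90 | 30–40% | 59–79% | 87–118% |
| 20, 45 | 84–113% | 167–225% | 247–333% |

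**The case against.** Ending research sampling when a child aged 2 or older is ready to leave is a defensible choice, and the objective is secondary. The windows are wide: only 60–75 and 120–135 min, about 30 minutes in all, are closed to a scheduled draw. The last window runs to 240 min, so some profiles will cover more than the nominal schedule. The half-life comes from adults given a spray. The gain shrinks when a sample has just been taken, and a rule with no minimum interval would draw 3 ml for almost nothing. All of this stands, and it limits the size of the point. None of it supplies a draw for a child in the closed intervals or requires one in the open windows.

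Three stronger readings are tempting but not supported:
- A reader might infer that every early discharge loses a sample. The windows show otherwise.
- A reader might infer that no slope is possible for a child ready at 70 min. That holds only if the 20-min sample precedes the decline phase. The plan does not settle this, and its Hypotheses call absorption rapid.
- A reader might infer that procedures differ in length of stay, so that a curve through the means would be badly biased, and that an exit draw would cure this. The Methods expect cases both under and over one hour, but the documents give no stay by procedure, no level by procedure and no plan to fit a curve through means. An exit draw at 70 or 130 min would not supply a 150-min level either; that bias is a matter for the analysis.

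**Conclusion.** The point holds as a cheap improvement to a secondary objective. The plan gives up late information that it could collect through a line already in place. How much an exit draw recovers depends on when the child is ready and when the previous draw was taken; the slope SE falls by between 19% and 50% in the cases worked above. It recovers part of what a complete profile would give, not all.

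These figures assume log-linear decline over the samples used. The coverage and absolute-precision figures also assume that the adult half-life is a fair guide for children, and the absolute SEs depend on an assumed residual CV of 10–30%. Without PACU times, the effect on the trial as a whole cannot be stated; only the effect per affected child can.

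**What to change.** Replace the stopping rule with wording such as:

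> If the patient is ready for discharge before sampling is complete, one final sample is drawn from the second IV as it is removed, in place of the remaining scheduled samples, unless a sample was taken shortly before (interval to be set by the sponsor, e.g. 15 min). Discharge is not delayed, and the actual time is recorded.

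This also settles what happens when a child is ready inside an open window.

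In the Statistical Analysis section, state that all samples are analysed by actual elapsed time since instillation, in one model across children, rather than through means at nominal times. A log-linear mixed-effects model with procedure as a covariate would serve. Children with only two late samples then still contribute. State which samples count as the decline phase. A rule requiring three post-peak samples for an individual half-life would not support the exit draw: counted from 45 min, it would still exclude the child ready at 70 min.

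The cost is one protocol sentence and a short analysis paragraph. Tube labels already carry the collection time. No needle stick is added, and the total stays within six draws and 18 ml. The downside is one 3 ml draw in some children who would otherwise have had fewer.

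### Pooling pledget placements up to five minutes apart, with no removal times, can misstate time since dosing and amount in place at the 5- and 10-minute plasma samples

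*Combined protocol and SAP*

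**What the plan says.** The rules for recording the drug are in Methods, in the paragraph on pledget placement:

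- Count: "The number of pledgets placed will be recorded at the time of insertion".
- Events: "If placement is separated by greater than five minutes, then this will be recorded as a separate event".
- Amount: "The volume at each time point and the total dose will be recorded". The only volume basis given is "10 pledgets in 15 ml of oxymetazoline (1.5 ml per pledget").

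Removal appears once, as the cue for scoring bleeding: "A four point scale to record subjective bleeding following removal of pledgets". Neither the time of removal nor the contact time is listed for collection.

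On the sampling side, Methods says: "Blood samples will be drawn at approximately 5 (3-6 min), 10 (8-12 min), 20 (18-22 min"), followed by samples at 45 (30-60), 90 (75-120) and 150 (135-240) minutes. Under Plasma Samples, the tube label carries the collection time. The secondary objective is to "measure the plasma concentrations of oxymetazoline at discrete time periods from instillation", relate them to hemodynamic effects and estimate how fast they fall.

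The document does not say which placement is time zero when there are several. It does not say what clock time a pooled event takes, or whether the five-minute gap runs from the first placement or from the previous one.

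**The concern.** The early draws have tight windows, but the dosing side is logged on a coarser clock. A pooling tolerance of five minutes equals the first nominal sampling time and is wider than the sampling tolerance of each of the first three samples. If some pledgets go in at the start and others a few minutes later within the same event, the 5-minute sample may be drawn before all the logged drug is in place.

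The Hypotheses describe absorption as fast and variable, and the first samples are the ones that must show this. Part of the apparent variability between patients could come from the log. With ten patients per procedure there is little room to average it out.

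The missing removal time is a separate gap. A soaked pledget left in place can go on supplying drug. A fall in level measured while pledgets are in place mixes input with elimination, and the planned data do not show which samples were drawn in that state. Times not written down on the day cannot be recovered later.

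**Working it through.** **The plan's own figure.** 15 ml / 10 pledgets = 1.5 ml per pledget, which agrees with the text.

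**Inputs from the document.** Pooling tolerance 5 min; sampling times and windows as listed in Methods; elimination half-life 1.72 to 2.32 h, from the adult study cited in Background and Significance.

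**Assumptions, not in the document.** Two equal placements at minutes 0 and 5, pooled and logged at minute 0; one event spans at most 5 min; absorption half-life between 5 and 30 min.

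**Step 1: timing.** The largest timing error as a share of nominal time is 5 / nominal time. The time from a placement at minute 5 to the sample is the window minus 5.

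**Step 2: amount.** With half the pledgets placed at minute 5, a sample drawn before then sees N/2 pledgets while the log shows N, and N / (N/2) = 2. With four pledgets, for illustration, the log shows 4 x 1.5 = 6 ml against 2 x 1.5 = 3 ml in place.

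**Step 3: effect on concentration.** Use a one-compartment model with first-order absorption, C(t) proportional to exp(-ke t) - exp(-ka t), and C(t) = 0 for t at or below 0. The true concentration relative to that implied by the pooled log is

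[0.5 C(t) + 0.5 C(t-5)] / C(t).

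Worked case: t = 10, absorption half-life 10 min (ka = 0.6931/10 = 0.0693 per min), elimination half-life 1.72 h = 103.2 min (ke = 0.6931/103.2 = 0.00672 per min).

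- C(10): 0.935 - 0.500 = 0.435
- C(5): 0.967 - 0.707 = 0.260
- Ratio: 0.5 + 0.5 x 0.260/0.435 = 0.80

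Over the full assumed range:

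| Sample (window), min | 5 / nominal | Sampling tolerance, min | Minutes since a placement at minute 5 | True / implied concentration |
|---|---|---|---|---|
| 5 (3-6) | 100% | -2/+1 | -2 to 1 | 0.50 at 3 and 5 min; 0.59-0.62 at 6 min |
| 10 (8-12) | 50% | -2/+2 | 3 to 7 | 0.77-0.84 |
| 20 (18-22) | 25% | -2/+2 | 13 to 17 | 0.90-0.98 |
| 45 (30-60) | 11% | -15/+15 | 25 to 55 | 0.97-1.02 |
| 90 (75-120) | 6% | -15/+30 | 70 to 115 | 1.00-1.02 |
| 150 (135-240) | 3% | -15/+90 | 130 to 235 | 1.01-1.02 |

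Beyond the first row, the last column is evaluated at the nominal time.

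**Step 4: check on the late samples.** In the elimination phase a 5-min shift changes concentration by 2^(5/139.2) - 1 = 2.5% (half-life 2.32 h) to 2^(5/103.2) - 1 = 3.4% (half-life 1.72 h).

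**Removal.** No arithmetic applies. The objective asks for a rate of decline, the pledgets are taken out at some point, and nothing collected locates that point relative to the samples.

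**The case against.** The strongest reply is that the exposure is narrow. The error needs several placements within one event, and the document does not say how often that happens. The two-fold figure is a particular case. Only the first two of six samples are materially affected. Plasma levels are a secondary objective; the primary one is hemodynamic, with blood pressure and heart rate taken every 5 minutes, so a five-minute event resolution matches the primary data. The Statistical Analysis section names no absorption model that needs minute-level dosing input. Recording the count when pledgets are inserted may also mean that each insertion is time-stamped.

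Most of this stands and limits the point to its present size. The time-stamp reading does not remove it: the event rule still pools those entries, and the text does not say which time the analysis would use.

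A reader might also infer three stronger things that the documents do not support:

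- **Later placements are ignored.** They are not. A placement at minute 25, say, would be its own event with its own volume. Since collection time is on the tube label, time since that placement can be worked out. No text imposes a single time zero.
- **Levels will appear to decline too slowly.** That presumes an analysis the plan does not describe. Untimed removal leaves input and decline mixed, but the documents do not establish the direction or size of any bias.
- **The dose-effect amounts are wrong.** Pooling leaves pledget count and total dose intact, and both the planned volume comparison and the hemostasis hypothesis concern the amount instilled. That volume is 1.5 ml times the pledget count is itself an inference. If so, it is a nominal loaded volume; saying so is a matter of labelling and changes no result. A constant delivered fraction would leave correlations unchanged, and the document gives no figure for variation in that fraction.

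**Conclusion.** The point holds as a limited weakness in recording that bears on a secondary objective. Where pledgets go in at several times within one event, time since dosing can be off by up to 5 minutes at the 5- and 10-minute samples, and the amount in place can be overstated. In the two-placement illustration, true concentration is about 50-62% of that implied by the log in the first window and 77-84% at 10 minutes. The effect is modest at 20 minutes and negligible from 45 minutes on.

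These sizes rest on the assumed absorption half-life, equal placements five minutes apart, a pooled event dated to its first placement, and a gap counted from that placement. If the gap is counted from the previous placement, one event could span more than five minutes. The gap in removal times does not depend on these assumptions: continuing absorption from pledgets in place cannot be told apart from the rate of decline. It would be too strong to say that early doses and times are wrong in general; they can be wrong, in patients with staggered placement.

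**What to change.** In Methods, replace the five-minute rule with an instruction to record the clock time and pledget count of every insertion and every removal, whatever the gap. In Statistical Analysis, state that the concentration-time and concentration-effect analyses use actual elapsed time from the first and from the latest placement, together with contact time. As an optional labelling change, call 1.5 ml times the pledget count a nominal loaded volume.

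The cost is slightly more recording in the operating room. Insertion is already being recorded, and removal is already observed because bleeding is scored then. Pledget use, blood sampling and sample size do not change.
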